5. DEPARTMENT OF MID WIFERY, HAWASSA COLLEGE OF HEALTH SCIENCE, HAWASSA, ETHIOPIA

Summary

Background: Anemia is the main cause of morbidity and mortality among pregnant women in developing countries with maternal and fetal consequences, which leads to premature births, low birth weight, fetal cognitive impairment and death.

Objective: To establish association between anemia and birth weight among pregnant women attending ANC clinic at public hospitals of Sidama region, Ethiopia, 2022..

Methods and materials: a prospective cohort study design will be conducted from March 1, 2022 to November 30, 2022 in public hospitals of Sidama region. A total of 12 Midwives and 6 supervisors will be involved in the data collection process. Exposed (pregnant women having anemia) and non-exposed (pregnant women not having anemia) will be selected by using simple random sampling technique from the prior three months ANC register of each selected public hospital

The data will be entered into Epidata software and exported to SPSS software for windows version 23 for analysis. Descriptive statistics will be computed and both bivariable and multivariable logistic regression will be employed to assess effect of anemia on birth weight among pregnant women. The output will be presented using adjusted odds ratio (AOR) with the respective 95% confidence interval (CI).

Work plan: The study will be conducted from March 1, 2022 to November 30, 2022.

Key words: anemia; birth weight; pregnancy.

Introduction

Background

Anemia is the main cause of morbidity and mortality among pregnant women in developing countries with maternal and fetal consequences [1], which leads to premature births [2], low birth weight [3], fetal cognitive impairment, and death [4].

There is an increased iron requirement during pregnancy due to greater expansion in plasma volume that results in a decrease in haemoglobin level to 11g/dl. Therefore, any hemoglobin level below 11g/dl in pregnancy is considered as anemia (5,6).

The prevalence of anemia among pregnant women is estimated to be 38% worldwide, 36.9% in Africa and 23% in Ethiopia [7,8]

The estimated prevalence of anemia among pregnant women in Ethiopia is high 63% compared to neighboring countries 55% in Kenya, 58% in Sudan and Eritrea 55.3% [9].

Low birth weight is not only a predictor of prenatal morbidity and mortality, but studies have found that it also increases the risk for non-communicable diseases such as diabetes mellitus and cardiovascular diseases in later life (10-11)

The global magnitude of LBW is 15.5 %. In Ethiopia, the prevalence of under-five mortality ranges from 53 to 169 per 1000 live births out of this neonatal mortality which is mainly attributed by LBW accounts the largest portion (12)

In multiple studies, different factors have been identified as determinant for LBW, and among these are young maternal age at pregnancy, birth order, the family's income, maternal under nutrition, maternal underweight, pregnancy related complications, preterm birth, chronic medical illness, multiple pregnancies, history of previous LBW, insufficient prenatal care, and maternal smoking (13 14 15 16).

Statement of problem

Consequences of anemia include increased maternal and perinatal mortality, impaired physical and cognitive development of children and reduced work productivity (9)

Severe anemia (<7 g/L) during pregnancy has been associated with major maternal and fetal complications. It increases the risk of preterm delivery, low birth weight, intrauterine fetal death, neonatal death, maternal mortality, and consequently infant mortality. (17)

Pregnant woman that live in rural areas [18], lack of raw vegetables in their diet [19], illnesses [18] and low levels of education [20] are also major determinants of anemia. Similarly, anemia prevalence decreases as wealth status increases [21.],

Further, studies conducted in Ethiopia have shown that the type of residence, gravidity, interval between pregnancies, and malaria infection during pregnancy have been associate with gestational anemia. (22)

Working to improve the nutritional status of pregnant women through supplementation of vitamin A, iron, and iodine is important to minimize the risk of anemia [23]

The reason of anemia during pregnancy in developing countries includes nutritional deficiencies of iron, folate, and vitamin B12 and parasitic diseases, such as malaria and hookworm. The relative contribution of each of these factors to anemia varies greatly by geographical location, season, and dietary practices [1].

The etiology of anemia is multifactorial with nutritional deficiencies (iron and folate), infectious diseases (hookworm, schistosomiasis, malaria and HIV) and genetic red blood cell disorders(sickle cell and thalassaemias) being key contributors[23].

In pregnant women, a favorable iron status is a prerequisite for a good course of pregnancy. There is evidence that iron deficiency, even in the absence of iron deficiency anemia, may have a negative impact in non-pregnant

women, e.g. in terms of decreased cognitive ability and physical performance [25]. In pregnant women it may impair fetal and infant development [24].

Low maternal hemoglobin levels are associated with increased risk of preterm delivery and low birth weight [26,27]. Prenatal prophylactic iron supplementation deserves further examination as a measure to improve birth weight and potentially reduce health care costs [28].

A randomized controlled trial suggested that prophylactic iron supplementation begun in early pregnancy can reduce third trimester anemia and improve birth outcomes [23]. However, a recent study showed that anemia during early pregnancy was not associated with increased risk of adverse perinatal outcomes, and anemia in later pregnancy was inversely associated with preterm birth and low birth weight [29].

The relationship between anemia and birth weight is still not clear. The previous study approaches in Sidama as well as in Ethiopia gave no evidence of a temporal relationship between exposure (anemia) and outcome (low birth weight) There is a gap to entirely infer causality between anemia and LBW.

The purpose of this study protocol is to investigate the association of anemia with birth weight among pregnant women attending ANC Clinic at Public Health Facilities of Sidama Region in the future

Significant of the study

Despite the efforts made by the government and other stakeholders, anemia during pregnancy is still a public health problem in Ethiopia. In Sidama, to the best of current knowledge, no research exists that has used prospective cohort study design to establish the association of anemia with birth weight. The finding of this study would help to guide the antenatal care service providers and other concerned stakeholders in Sidama Region to work more on prevention and control of anemia and low birth weight

Literature Review

Risk factors of Low Birth Weight (LBW)

A matched Case Control study conducted in Malaysia, after multivariable conditional logistic regression analysis identified younger maternal age, previous history of LBW infants, prematurity, and current hypertension as significant factors associated with LBW infants (30).

Registry-based retrospective cohort study conducted in Northern Tanzania showed that preeclampsia, eclampsia, chronic hypertension, maternal anemia, HIV status, smoking during pregnancy, caesarean section delivery, placental abruption, placenta Previa, PROM, maternal underweight, obesity and female gender of baby were significantly associated with delivery of low birth weight infants (31).

A cross-sectional study conducted in Kenya showed that delivery of LBW baby in a previous birth and female infant were independently associated with LBW (32). Another retrospective analysis of cohort study conducted in Kenya also found that increasing parity was associated with reduced odds of LBW (33).

According to a meta-analysis of 895 studies conducted by Kramer, birth weight is governed by two major processes: duration of gestation and intrauterine growth rate. Factors with well-established direct causal impacts on intrauterine growth include infant sex, racial/ethnic origin, maternal height, pre-pregnancy weight, paternal weight and height, maternal birth weight, parity, history of prior LBW infants, gestational weight gain and caloric intake, general morbidity and episodic illness, malaria, cigarette smoking, alcohol consumption, and tobacco chewing. In developing countries, the major determinants of IUGR are Black or Indian racial origin, poor gestational nutrition, low pre-pregnancy weight, short maternal stature, and malaria. For gestational duration, only pre-pregnancy weight, prior history of prematurity or spontaneous abortion and cigarette smoking have well established causal effects (34).

A follow up study conducted in Malawi also found a positive association between maternal HIV infection and LBW. HIV infection was strongly associated with LBW after adjusting for potential confounders. In similar study multivariate analyses of mean birth weight revealed a 138-g reduction in birth weight by HIV infection (35). Another study conducted Malawi also indicated that, HIV positive mother had 1.77 times more likely than

HIV negative mothers to give birth to LBW infant (36). Maternal HIV infection was also associated with 2 times increased chance of LBW in Kenya (37).

Studies conducted in different parts of Ethiopia showed different factors to be associated with LBW. For instance a case-control study conducted in Bale zone, Ethiopia also showed that maternal age at delivery less than 20 years and residing in rural area were socio-economic variables associated with low birth weight. Maternal risk factors like occurrence of health problems during pregnancy, maternal BMI less than 18 kg/m², maternal height less than 1.5m, inter-pregnancy interval less than 2 years, absence of ANC and history of khat chewing were also associated with low birth weight (38).

An observational cohort study on pregnant women conducted in Kersa, Ethiopia, also showed that LBW is significantly associated with maternal mid upper arm circumference (MUAC) less than 23 cm and not attending ANC (39).

Association between Anemia and LBW

A review of different literature showed that association between anemia and birth weight among pregnant mothers.

According to a facility based case-control study conducted in Ahmadabad city, India, showed there is relationship between use of anemia and LBW. According to this review anemia were found to be significant independent risk factor for LBW (40).

A hospital based retrospective cohort study conducted among infants born to HIV-infected women in public hospitals in Northwest Ethiopia showed maternal anemia was significantly associated with LBW(41).

[figure not shown]

Figure 1 Conceptual framework showing birthweight and associated factors among pregnant women attending ANC clinic in Sidama Region, 2022. Developed from different literatures reviewed

Objective

To establish association between anemia and birth weight among pregnant women attending ANC clinic at public hospitals of Sidama region, Ethiopia, 2022.

Methodology

Study area

The study will be conducted in public health facilities of Sidama national regional state. It is located about 275 Kilometers away from Addis Ababa. It has 30 Districts, 1 city administration and 6 town administration with a total of 576 kebeles of which 524 of them are rural and 52 are urban. It is one of the highly populated areas in Ethiopia, having a total population of about 4 million people residing on 72100 hectare of land. Out of the total population 5.7% are urban and 94.3% rural residents. Sidama is characterized by three agro-ecological zones: the dry midlands/lowlands (20%), the midlands (48%) and the highlands (32%). In Sidama region mixed agriculture (crop and livestock production) is practiced. Major crops grown include: enset, coffee, maize, wheat, teff, barley, haricot bean and khat. Enset is the main staple crop both in highlands and midlands while maize is so in the lowlands. There are two cropping seasons in Sidama Zone: belg and meher. Belg rains are mainly used for land preparation and planting of long cycle crops such as maize and sorghum and seed bed preparation for meher crops. The meher rains are used for planting of cereal crops like barley, teff, wheat and vegetable crops. Besides, meher rains are also responsible for the growth and development of perennial crops such as enset,

coffee and khat. Food security is more precarious in the lowland areas of Aleta Wondo, Borecha, Darra, Bensa, Loka Abaya and Hawassa Zuria woredas mainly due to moisture stress and water logging in some pocket areas hampering agricultural production, less diversification of food sources and minimum use of improved farm inputs due to lack of cash and credit facilities to purchase the inputs. The Sidama region administration has a total of 4063 health professional of different disciplines and 524 Health Posts, 127 Health Centers, 1 general and 12 District hospital owned by government and additionally there are 21 private and 3 NGO clinics, 65 private rural drug venders. The overall potential health service coverage of the Zone by public health facilities are 90.3%.

Study design

a prospective cohort study design will be conducted from March 1 2022 to November 30 2022

Source population

All pregnant women attending ANC clinic at public hospitals of Sidama region.

Study population

Pregnant women selected by using simple random sampling technique from the prior three months ANC register of selected public hospitals and meet inclusion criteria

Eligibility criteria

Inclusion Criteria

Attend ANC in the last 3 months

Permanent residence with possible contact

Plan to deliver in the region

Exclusion Criteria

Severe anemia / sever illness

Sample size determination

Sample size calculation for the second objective

The sample size for Exposed and Non-Exposed is calculated using Epi Info version 7 soft-ware by taking a proportion of low birth weight among non anemic women of 14.6%, AOR of 3.17, study power of 80%, an Exposed to Non-Exposed ratio of 1:1 and a non-response rate of 15%. Finally a total of 180 (90 Anemic mothers and 90 non-anemic mothers) sample size was calculated.

Table 1: Sample size calculation

| Factors | Ratio of controls to cases | % of outcome in unexposed | AOR | Power | CI | Exposed | Non Exposed | Final sample size | Source |
|---------|----------------------------|---------------------------|------|-------|-----|---------|-------------|-------------------|---------|
| Anemia | 1:1 | 14.6 | 3.17 | 80 | 95% | 78 | 78 | 156 | AZ |
| Anemia | 1:1 | 11.2 | 3.81 | 80 | 95% | 68 | 68 | 136 | Sodo |
| Anemia | 1:1 | 13.02 | 3.51 | 80 | 95% | 70 | 70 | 140 | Kembata |

Sampling techniques

From 18 public hospitals found in the region we randomly selected 6 hospitals. Enumeration of prior three month's ANC register was conducted. Then, based on the number of ANC register, the sample size was proportionally allocated for all selected public hospitals in the region (Figure 1).

Exposed (pregnant women having anemia) and non-exposed (pregnant women not having anemia) will be selected by using simple random sampling technique from the prior three months ANC register of each selected public hospital and followed until delivery to see the incidence of low birth weight.

[figure not shown]

Figure 2: Schematic representation of sampling procedure

Study variables

Dependent variable: Birth Weight

Independent variable

- Socio-demographic factors
- Reproductive related
- Medical related
- Health promotion
- Anemia

Operational definitions

Anemia: any hemoglobin level below 11g/dl in pregnancy is considered as anemia (5,6).

Weight (Kg): will be measured by electronic scales with digital display (UNICEF SECA Electronic weight scale (± 10 precision scale) and Participants will be asked to remove their shoes and any bulky clothing during measurement will be taken.

Height (m): will be measured using a portable stadiometer with a sliding head plate, a base plate and connecting rods marked with a measuring scale. Participants will be asked to remove their shoes.

Birthweight: birthweight of newborn is the first weight of the newborn obtained after birth. Newborn birth weight is normal if it is $\geq 2,500$ g. And lower birth weight if it is $< 2,500$ g irrespective of the gestational age (42)

Intestinal parasite: presence of ova/parasite of hookworm, *Tenia* species, *Ascaris lumbricoides* and *S.stercoralis*

IPV: A behavior within an intimate relationship that is bound to result in physical, sexual, or psychological harm to the other partner or spouse (43).

Data collection procedure

A Data will be collected using a structured questionnaire and anthropometry measurements

A total of 12 Midwives and 6 supervisors will be involved in the data collection process.

The questionnaire included information on socio-demographic factors and obstetrics characteristics.

Anthropometric assessment

Height measurement will be performed with the aid of a measuring tape. The respondents will be asked to remove footwear, hair accessories that may obstruct measurement. A ruler will be placed on top of their heads, and the reading will be taken from the top of the ruler at eye level. Height will be then read and recorded to the nearest 0.1 cm. A calibrated bathroom scale will be used to measure weight. The device will be placed on a level surface. Each respondent will be asked to stand at the centre of the scale, barefoot with minimal clothing and empty pockets. The weight will be recorded to the nearest 0.1 kg.

To reduce intra individual error, height and weight will be measured twice and the mean value will be used for analysis. Anthropometric indices will be calculated using WHO Anthro software version 3.2.2.

Measurement of Birth weight

Data for birth weight will be recorded using the metric scale (in grams). During data collection, birth weight will be confirmed by weighing the baby using the metric scale (in grams). Documented evidence on the child health card or verbally from the mother will only be used if the baby is ill.

Data quality control

Three day intensive training will be given on how to perform standardized height and weight measurement and on interviewing techniques using standard checklist and structured questionnaire. The checklist and questionnaires will be translated into a regional working language (Sidamu Affo). Supervision will be conducted. Double data entry will be done and the questionnaire will be pretested on 5 % of total sample size at Dilla city. The calibrated instrument will be used to measure height and weight.. During data collection, continuous supervision will be done by the supervisors and principal investigator.

Data processing and analysis

The data will be entered into Epidata software and exported to SPSS software for windows version 23. for analysis. Descriptive statistics will be computed and both bivariable and multivariable logistic regression will be employed to identify effect of anemia on birth weight Independent sample student t test will be used to compare the mean difference in birth weight in anemic and non-anemic pregnant women. Multi variable Logistic Regression will be done to establish association of anemia with birth weight.

Ethical consideration

Prior to data collection appropriate ethical clearance and supportive letter will be obtained from the Ethical Review Committee of Hawassa College of Health Science. Written permission will be obtained to undertake the study from the selected hospitals. Participation in the study will be based on voluntary base and the participants

will be informed about the right to withdraw at any time from the study. Confidentiality will be assured by using anonymity. Pregnant women who had anemia (Hb<11g/dl) will be provided with Iron-folate tablets. Written consent will be requested from every study participant included in the study during data collection time after explaining the objectives of the study. For this purpose, a one page consent letter was attached to the cover page of each questionnaire stating about the general objective of the study and issues of confidentiality which was discussed by the data collectors before proceeding with the interview.

Work plan

Table 2 : Showing the work plan of the study in Sidama Region, 2022

| Activity | Oc t | Nov | De c | Jua n | Fe b | Mar | Ap r | May | Ju n | Jul | Au g | Se p | Oc t | No v | De c |
|---------------------------------------|---------|-----|---------|----------|---------|-----|---------|-----|---------|-----|---------|---------|---------|---------|---------|
| Research proposal Preparation | | | | | | | | | | | | | | | |
| Final proposal submission and Defense | | | | | | | | | | | | | | | |
| Obtaining ethical Clearance | | | | | | | | | | | | | | | |
| Giving training | | | | | | | | | | | | | | | |
| Data collection and processing | | | | | | | | | | | | | | | |
| Final paper Submission | | | | | | | | | | | | | | | |
| Defense and dissemination of result | | | | | | | | | | | | | | | |

Questionnaire on birth weight

Socio-demographic characteristics of pregnant women public health facilities (N=180).

| Variables | Coding categories | Skip |
|--|---|-------------|
| Age | _____ | |
| Residence | 1. Rural 2. Urban | |
| Marital status | 1. Never married 2. Married 3. Separated/Widowed | |
| Religion | 1. Orthodox 2. Catholic 3. Protestant 4. Muslim 5. (Specify) | |
| Highest Educational level | | |
| Highest Husband Educational level | _____ | |
| Occupation status | 1. Government employee 2. Private employee 3. Merchant 4. House wife 5. (Specify) | |
| Family income | _____ | |
| Family size | _____ | |
| Sex of the newborn | 1. Female 2. Male | |
| Obstetric and baby characteristics of mothers who gave birth at the selected public Hospitals | | |
| Current pregnancy type | 1. Planned 2. Unplanned | |
| Gravidity | | |
| Fertility desire | | |
| Injury history of any source | 1. Yes 2. No | |
| Trimester at 1st visit for the last pregnancy | 1. 1 st 2. 2 nd 3. 3 rd | |
| TT vaccine before or during pregnancy | 1. Yes 2. No | |

| | | |
|---|---|--|
| Iron supplementation for current pregnancy | 1. Yes 2. No | |
| Dietary counseling during the current pregnancy | 1. Yes 2. No | |
| Extra meal during current pregnancy | 1. Yes 2. No | |
| History of abortion | 1. Yes 2. No | |
| History of still birth | 1. Yes 2. No | |
| Obstetric and baby characteristics of mother who gave birth at the selected public Hospitals | | |
| APH during the current pregnancy | 1. Yes 2. No | |
| Substance use during the current pregnancy | 1. Yes 2. No | |
| Alcohol use during the current pregnancy | 1. Yes 2. No | |
| Chronic medical illness | 1. Yes 2. No | |
| Reproductive characteristics of respondents | | |
| Used modern contraceptive | 1. Yes 2. No | |
| Time to book first ANC visit | 1. ≤ 16 weeks 2. > 16 weeks | |
| Number of ANC visit | 1. ≤ 3 visit 2. ≥ 4 visit | |
| Number of birth (parity) | | |
| Birth interval between last birth to previous one | 1. < 2 year s 2. > 2 years | |
| History of PROM | 1. Yes 2. No | |
| IPV during violence | 1. Yes 2. No | |
| Gestational age | 1. < 37 weeks 2. > 37 week | |
| Alive number of children | 1. ≤ 2 children 2. ≥ 3 children | |
| VDRL | 1. Nonreactive (-ve) 2. Reactive (+ve) 3. Unknown | |
| Hemoglobin status | _____ | |
| Bad obstetric history | 1. Yes 2. No | |

| | | |
|--|---|--|
| Degree of severity of anemia | 1. No anemia 2. Mild 3. Moderate 4. Severe | |
| Complication of neonate | 1. Yes 2. No | |
| Congenital malformations | 1. Yes 2. No | |
| Ever smoked during the current pregnancy | 1. Yes 2. No | |
| Any person smoked in the surroundings | 1. Yes 2. No | |
| Previous history of LBW | 1. Yes 2. No | |
| Pregnancy complication | 1. Yes 2. No | |
| HTN | 1. Yes 2. No | |
| Malaria during pregnancy | 1. Yes 2. No 3. | |
| MUAC | _____ | |
| Weight | _____ | |
| Height | _____ | |

Reference

4. Kalaivani K. Prevalence & consequences of anemia in pregnancy. *Indian J Med Res*. 2009;130(5):627–33, Walter T. Effect of iron-deficiency anemia on cognitive skills and neuromaturation in infancy and childhood. *Food Nutr Bull*. 2003;24(4):104–10
5. Susan T and Blackburn DO. Maternal, Fetal, & Neonatal Physiology: A Clinical Perspective. *Qualitative Health Research*. 2007; 11(6): 780-794.

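### The total of 180 falls slightly short of covering the stated 15% non-response: 153 women are expected to remain against the 156 required (minor arithmetic error)

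*Protocol*

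**What the plan says.** Protocol, Sample size determination, gives the inputs in the text: "taking a proportion of low birth weight among non anemic women of 14.6"%, an odds ratio of 3.17, "study power of 80"%, "an Exposed to Non-Exposed ratio of 1:1" and "a non-response rate of 15"%. It then gives the result as 180 women, 90 in each group: "a non-response rate of 15%. Finally a total of 180 (90 Anemic mothers and 90 non-anemic mothers) sample size was calculated".

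The first row of Table 1 carries the same inputs and gives 78 per group and 156 in total: "Anemia | 1:1 | 14.6 | 3.17 | 80 | 95% | 78 | 78 | 156 | AZ". The column holding the 156 is headed as the final sample size, while the text above the table gives 180 as the final figure.

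The questionnaire heading also uses 180: "Socio-demographic characteristics of pregnant women public health facilities (N=180").

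Under Sampling techniques, the sample size is allocated in proportion across six hospitals, and women are drawn at random from the antenatal registers and followed to delivery. The protocol describes no replacement of women who do not respond.

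**The concern.** A non-response allowance should leave the required number once the stated fraction has failed to respond. If a fraction d of the women selected does not respond, N selected women leave N(1 − d), so the number to select is n/(1 − d). Multiplying n by (1 + d) gives a smaller number that does not restore n.

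The stated 180 agrees with the multiplied figure and not with the divided one. If so, the plan does not quite reach its own target under its own non-response rate, and the 80% power attached to the total is slightly overstated. What is at stake is the accuracy of the sample-size statement, which would be carried into the study report. The two figures that are both presented as final, 156 and 180, add some confusion.

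**Working it through.** **Inputs** (Protocol, Sample size determination and Table 1, first row): p0 = 0.146; odds ratio 3.17; power 80%; 95% confidence; ratio 1:1; non-response 15%. Assumption: the 95% is taken as a two-sided 5% level, which is what reproduces the table.

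**1. Reproduce the 156.**

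- Proportion in anemic women: p1 = 3.17 × 0.146 / (0.854 + 3.17 × 0.146) = 0.4628 / 1.3168 = 0.3515. The difference is Δ = 0.2055 and the mean proportion is p̄ = 0.2487.
- Uncorrected size per group: n′ = [1.960 √(2p̄(1 − p̄)) + 0.842 √(p0(1 − p0) + p1(1 − p1))]² / Δ² = 68.3, so 69.
- With continuity correction: n = (n′/4) × [1 + √(1 + 4/(n′Δ))]² = 77.7, so 78 per group and 156 in total. This is the Table 1 figure.
- The same corrected formula gives 67.2 and 69.7 for the other two rows, so 68 and 70, again as tabulated. Table 1 therefore rests on the continuity-corrected formula and includes no non-response allowance.

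**2. Reproduce the 180.**

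| Operation | Total | Per group |
|---|---|---|
| Multiply by 1.15 | 156 × 1.15 = 179.4, so 180 | 78 × 1.15 = 89.7, so 90 |
| Divide by 0.85 | 156 / 0.85 = 183.5, so 184 | 78 / 0.85 = 91.8, so 92 |

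The first line matches the protocol in total and per group. That multiplication was used is an inference from this match.

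**3. Check the 180 directly.** This step does not depend on how 180 was reached.

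- 180 × 0.85 = 153, or 76.5 per group, against 156 required: 3 short.
- 184 × 0.85 = 156.4, which keeps the 156.
- Largest non-response that 180 covers: 1 − 156/180 = 13.3%.
- Difference in the number to select: 184 − 180 = 4, and 4/180 = 2.2%.

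**4. Power at the expected number** (p0 = 0.146, p1 = 0.3515, two-sided 5%). The corrected figures are obtained by inverting the formula in step 1.

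| Women remaining | Continuity-corrected | Uncorrected |
|---|---|---|
| 156 (78 per group) | 80.2% | 85.0% |
| 153 (76.5 per group) | 79.3% | 84.3% |

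The cost of the shortfall on the plan's own formula is 80.2 − 79.3 = 0.9 percentage points, which leaves power 0.7 points below the stated 80%.

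**The case against.** The strongest reply is that this makes no practical difference.

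- The plan sizes on the most demanding of three scenarios (156, against 136 and 140). With 153 women, corrected power is about 85.6% under the second row and 84.1% under the third.
- Without the continuity correction, the first row needs only 69 per group (138), and 153 exceeds that comfortably.
- A true odds ratio of 3.20 in place of 3.17 would bring 76.5 per group back to 80%. That shift is far smaller than the range of 3.17 to 3.81 in Table 1.

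All of this stands as an argument about size. It does not make the statement correct, because the row and the formula are the ones the plan itself chose, and on those 180 does not quite deliver the stated figure.

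It is also fair to say that the protocol never shows the operation. The multiplication should be reported as likely; the shortfall of 153 against 156 holds either way.

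The allowance is for non-response, and the protocol gives no rate for loss during follow-up. A reader might infer that the plan mishandles attrition, or that it assumes 15% loss to follow-up. The text supports neither reading, so the point should be confined to non-response.

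**Conclusion.** The sample-size statement is wrong as written, by a small amount. At the stated 15% non-response, 180 women leave 153 where 156 are needed; the allowance calls for 184, and 180 covers non-response of up to 13.3%. Expected power is about 79% on the formula behind Table 1, and about 84% without the continuity correction.

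This rests on three assumptions: that 15% means 15% of the women selected, that non-responders are not replaced (no replacement is described), and that the test level is two-sided 5%.

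A reader might infer that the study is materially underpowered. The figures do not support that: the change in power is under one percentage point, and the other two rows of Table 1 keep more than 80% with 153 women. This is a low-priority correction.

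**What to change.** Correct the statement without adding women. In Sample size determination, after the total of 180, write for example:

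> With 180 women selected and 15% non-response, 153 are expected, giving about 79% power (continuity-corrected, odds ratio 3.17; about 84% without the correction).

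In Table 1, relabel the column holding the 156 as the number needed before the non-response allowance, so that it no longer competes with the 180 in the text.

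If the sponsor prefers to keep the 80% claim at 15% non-response, the total to select is 184 (92 + 92), and the N in the questionnaire heading changes with it.

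The first option costs one sentence and one column label, and the stated power becomes about 0.7 points less favourable. The second costs four more women.
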